4.1.1 Initial Dosing and Safety Assessment

As this study is novel in the use of combined prostanoid therapy, the Sponsor intends to limit study site start-up and subject recruitment activities during the first six months. Study site selection during this period will be based on site experience with prostanoid therapy and the conduct of clinical studies. As such, a minimum number of subjects will initially be exposed to combined prostanoid therapy.

The independent Data Safety Monitoring Board (DSMB), in accordance with the charter, reviews unblinded study data during scheduled review meetings to ensure adequate subject safety to the combined exposure of BPS-314*d*-MR and inhaled treprostinil. No new safety signals have been detected thus far.

4.1.2 Optional Plasma Concentration Assessment

An optional plasma concentration assessment will be offered at study sites that are capable of collecting, processing and storing samples, are approved by the Sponsor and agree to participate. Subjects within those sites will decide if they wish to participate in the optional plasma concentration assessment. Subjects electing to participate will have blood drawn at the following time points: A trough sample (15 minutes pre-dose, \pm 5 minutes) at the Week 4 Visit, and four

blood samples (around the second daily dose of study drug) during Week 12 (first Quarterly Visit) at 15 minutes pre-dose, and 15 minutes, 1 hour and 2.5 hours post-dose (\pm 5 minutes), and, if feasible, for SAEs for measurement of BPS-314*d* and treprostinil plasma concentrations. Dosing times should be documented in the subject's source documentation. Unwillingness to participate in the optional plasma concentration assessment will not affect the subject's or the site's participation in the study.

See Appendix 1 Study Events Table.

4.1.3 Optional Hemodynamic Assessment

An optional hemodynamic assessment will be offered at study sites capable of conducting hemodynamic procedures, are approved by the Sponsor and agree to participate. Subjects at selected research centers may elect to volunteer in the sub-study until the Sponsor closes enrollment. Hemodynamic measurements, such as mean pulmonary arterial pressure, cardiac index, and pulmonary vascular resistance, will be assessed by right heart catheterization (RHC). For those subjects consenting to the RHC, the procedure will be performed at the Baseline Visit (within 0-21 days prior to the scheduled Baseline Visit) and at the Month 6 Quarterly Visit (or within 7 days before or after). During the Baseline assessment the RHC should be performed at peak study drug dosing. At the Month 6 Quarterly Visit the RHC should be performed at peak study drug blood levels (1-2 hours, ± 15 minutes, after the study drug is administered).

4.2 Rationale for Study Design and Control Group

This is a randomized, double-blind, placebo-controlled study with a parallel group design. Randomization will avoid potential bias in the assignment of subjects to treatment arms and will increase the likelihood that unknown and known subject characteristics (e.g., demographics and disease characteristics) are evenly balanced across the two arms. Double-blind treatment is used to reduce potential bias in dosing, therapeutic decisions, and data handling. The placebo control group allows all subjects to receive similar treatment paradigms and serves as a direct reference group for assessing the effect of study drug. The parallel (control)-group design allows the direct comparison of the two treatment groups with minimal confounding of time and reduces the potential that improvements in measures of efficacy from baseline are merely due to the fact that subjects are involved in a clinical intervention during the course of the study.

4.3 Study Duration and Dates

As the trial is intended to continue until the specified number of Clinical Worsening Events (113) has occurred, the duration of treatment for individual subjects will vary. The maximum duration of treatment for any individual subject is expected to be 3 years, with the anticipated date for last subject last study visit in Q2 2016.

5 STUDY POPULATION SELECTION

5.1 Study Population

The study population is comprised of males and females with PAH, age 18 to 80 years, inclusive, presently on a stable regimen of inhaled treprostinil.

5.2 Inclusion Criteria

The following are inclusion criteria to be enrolled in this study:

- 1. Male or female, age 18 to 80 years (inclusive).
- 2. Established diagnosis of pulmonary arterial hypertension that is either idiopathic or familial PAH, collagen vascular disease associated PAH, PAH associated with HIV infection, PAH induced by anorexigens/toxins, or PAH associated with repaired congenital systemic-to-pulmonary shunts (repaired ≥1 years).
- 3. If HIV positive, has a CD4 lymphocyte count ≥200 cells/mm3 within 30 days of Baseline Visit and is receiving current standard of care anti-retroviral or other effective medication.
- 4. At the Screening Visit, WHO functional class III or IV and who have declining or unsatisfactory clinical response to current PAH therapy.
- 5. At the Baseline Visit, WHO functional class III or IV and who have declining or unsatisfactory clinical response to inhaled treprostinil therapy.
- 6. Able to walk unassisted (oxygen use allowed).
- 7. A 6-Minute Walk distance (6MWD) of \geq 100 meters at the Screening Visit.
- Previous (within five years prior to the Baseline Visit) right heart cardiac catheterization (RHC) with findings consistent with PAH, specifically mean Pulmonary Arterial Pressure (PAPm) ≥25 mmHg (at rest), Pulmonary Capillary Wedge Pressure (PCWP) (or left ventricular end diastolic pressure) ≤15 mmHg, and Pulmonary Vascular Resistance (PVR) >3 mmHg/L/min.¹
- 9. Echocardiography excluding any clinically significant left heart disease (e.g. left sided valve disease, wall motion abnormality suggesting of myocardial infarction, left ventricular hypertrophy, etc.).
- 10. Pulmonary function tests conducted within 12 months before or during the Screening period to confirm the following:
 - a. Total lung capacity (TLC) is at least 60% (predicted value); and
 - b. Forced expiratory volume at one second (FEV1) of at least 50% (predicted value).
- 11. Subjects receiving additional FDA approved PAH therapies must be stable on their current dose for at least 30 days prior to the Baseline Visit, apart from modification of anticoagulant or diuretic dosages.
- 12. Must have completed 90 days of uninterrupted inhaled treprostinil treatment and received a stable dose of inhaled treprostinil for at least 30 days prior to Baseline to be eligible for randomization into the study.
- 13. Women of child-bearing potential (defined as less than 1 year post-menopausal and not surgically sterile) must be practicing abstinence or using two highly effective methods of contraception (defined as a method of birth control that result in a low failure rate, i.e., less

¹ For conflicting RHCs, the most recent assessment is preferred if relevant in Investigator's judgment.

than 1% per year, such as approved hormonal contraceptives, barrier methods [such as a condom or diaphragm] used with a spermicide, or an intrauterine device). Subject must have a negative pregnancy test at the Screening and Baseline Visits.

14. Willing and able to comply with study requirements and restrictions.

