1.3 Study Rationale

Intravenous prostacyclin therapy prolongs survival in patients with PAH (Barst 1996), and it is considered by many clinicians as the "gold standard" of care. As more therapies have emerged for PAH treatment, prostacyclin therapy has evolved, now with inhaled formulations available and oral formulations under development.

Parenteral prostacyclins are typically reserved until later in the course of disease due to risks and challenges associated with this route of administration.

The rationale for the use of BPS-314*d*-MR as an add-on oral therapy to inhaled treprostinil in subjects with PAH is based upon the quantitative differences observed in their mechanism of action and more specifically their complementary pharmacokinetic profiles.

Inhaled treprostinil and oral BPS exhibit independent pharmacokinetics. Inhaled treprostinil is characterized by rapid absorption and a relatively short half-life, whereas BPS-314*d*-MR demonstrates lower peak plasma concentrations, slower absorption, and a more protracted elimination from the circulation.

Pharmacokinetic modeling of their respective profiles, suggested that the proposed combination of inhaled treprostinil and BPS-314*d*-MR given together, might provide a less invasive, tolerable and clinically beneficial approach to achieving sustained prostacyclin exposure, approximating the desired profile observed with continuous intravenous delivery. Pharmacokinetic modeling used actual PK data for BPS-314*d* from Study BPS-314*d*-MR-PAH-101, evaluating 15 μ g and 30 μ g dose, QID along with predicted PK data for combination administration with inhaled treprostinil to gain an understanding of the concentration-time profiles and how they might influence the safety and efficacy of both drugs.

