1.4 Clinical Hypothesis

Treprostinil, inhaled (Tyvaso®) is a registered treatment for PAH with an acceptable safety profile. Oral BPS-314*d*-MR is under development as a prostacyclin for the treatment of PAH. This study is designed to leverage the complimentary mechanistic and pharmacokinetic differences between locally acting inhaled treprostinil and the systemic delivery of BPS-314*d*-MR, creating an effect that more closely approximates parenteral therapy than using either therapy alone. This study will test the hypothesis that combining these therapies will achieve a more effective and longer lasting therapeutic effect, delaying time to clinical worsening.

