2 STUDY OBJECTIVES

2.1 **Primary Objective**

The primary objective of this study is to compare the effect of BPS-314*d*-MR versus placebo added to treprostinil, inhaled (Tyvaso®) on the composite endpoint of time-to-clinical-worsening (TtCW), defined as the time from randomization to the first of any of the following clinical worsening events:

- Death (all causes)
- Hospitalization due to worsening PAH defined as:
 - Non-elective hospitalization lasting at least 24 hours in duration caused by clinical conditions directly related to PAH and/or right heart failure and requiring intensification of treatment; or
 - Lung or heart / lung transplantation; or
 - Atrial septostomy
- Initiation of a parenteral (infusion or sub-cutaneous) prostacyclin, directly related to worsening PAH (transient use [≤ 7 days] for non-PAH related illness allowable)
- Disease progression (all criteria required):
 - A decrease in six minute walk distance (6MWD) of at least 15% from Baseline (defined as the average of the two 6MWTs performed on sequential days of the Baseline Visit), or being too ill to walk as a consequence of PAH progression, confirmed by six-minute walk tests (6MWT) performed at 2 consecutive visits
 - Worsening of PAH symptoms, which must include either:
 - An increase in WHO Functional Class or
 - Worsening symptoms of right heart failure
- Unsatisfactory long-term clinical response (all criteria below required):
 - Receiving randomized treatment for at least 24 weeks
 - A decrease of at least 15% from Baseline (defined as the average of the two Baseline Visit 6MWTs) in 6MWD, or too ill to walk, directly related to PAH progression, at Week 24 and beyond; at 2 consecutive visits, and
 - Sustained WHO Functional Class III or IV symptoms for at least 24 weeks.

The Investigator will initially judge whether a suspected clinical worsening event has occurred based on the definition provided above. An Event Adjudication Committee (EAC) will review all suspected clinical worsening events and make a final determination. The EAC will be composed of medical experts in the PAH field, will be independent from the Sponsor, and will assess each event in a blinded fashion. Specific details regarding the Committee's membership, processes and procedures will be outlined in the EAC charter.

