Subjects will continue participation in the study until it is formally concluded by the Sponsor. Subjects are expected to remain on study drug throughout their participation in the study unless/until IV or SQ prostanoid therapy is added or in the event of lung transplantation. If a subject discontinues the study for any reason prior to the formal conclusion of the study by the Sponsor, the subject will be asked to return to the clinical for an End of Study (Early Termination) Visit. Vital status will be assessed for all randomized subjects at the formal conclusion of the study. For randomized subjects who terminate early, vital status will be assessed three months following discontinuation unless the formal conclusion of the study occurs within the three month time period.

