5.3 Exclusion Criteria

Patients who meet any of the following criteria will be excluded from the study:

- 1. Pregnant or lactating.
- 2. Has previous experience with beraprost or BPS-314*d* (i.e., BPS-IR, BPS-MR or BPS-314*d*-MR).
- 3. PAH related to any condition not covered under inclusion criteria, including but not limited to pulmonary venous hypertension, pulmonary veno-occlusive disease, pulmonary capillary hemangiomatosis, or chronic thromboembolic pulmonary hypertension.
- 4. History of interstitial lung disease, unless subject has collagen vascular disease and has had pulmonary function testing conducted within 12 months of the Baseline Visit demonstrating a total lung capacity ≥60% of predicted.
- 5. Has active hemorrhagic condition (e.g., upper digestive tract hemorrhage, hemoptysis, etc.), or has a pre-existing condition that, in the Investigator's judgment, may increase the risk for developing hemorrhage during the study (e.g., hemophilia). Transient hemorrhage (e.g., epistaxis, normal menstrual bleeding, gingival bleeding, hemorrhoidal bleeding, etc.) will not preclude enrollment.
- 6. Has received any investigational drug, device or therapy within 30 days prior to the Baseline Visit or is scheduled to receive another investigational drug, device or therapy during the course of the study.
- 7. Has any musculoskeletal disease or any other disease that would significantly limit ambulation.
- 8. Has any form of unrepaired or recently repaired (< 1 year) congenital systemic-topulmonary shunt other than patent foramen ovale.
- 9. Evidence of significant coronary arterial disease with symptoms, such as angina.
- 10. Left sided myocardial disease as evidenced by left ventricular ejection fraction < 40%, or shortening fraction < 22%.²
- 11. Has creatinine clearance <30 (using the Crockroft-Gault formula) or requires hemodialysis.
- 12. Has Childs-Pugh class C liver cirrhosis.
- 13. Has had previous atrial septostomy.
- 14. Any other clinically significant illness or abnormal laboratory values (measured during the Screening period) that, in the opinion of the Investigator, might put the subject at risk of harm during the study or might adversely affect the interpretation of the study data.³
- 15. Anticipated survival less than 1 year due to concomitant disease.

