7.12.8 Treatment-Emergent Adverse Events

Treatment-emergent AEs will be defined as events that are newly occurring or worsening from baseline following treatment with study drug.

BPS-314*d* is the active component of BPS-MR. The most frequently reported treatment emergent adverse reactions ($\geq 10\%$) are headache, nausea, diarrhea, flushing, jaw pain, dizziness, pain in extremity, palpitations, pain, fatigue, vomiting, and hot flush.

The most common adverse reactions ($\geq 10\%$) with Tyvaso are cough, headache, nausea, dizziness, flushing (blushing of the skin), throat irritation, pharyngolaryngeal (pharynx and the larynx) pain and diarrhea.

Prostacyclins, as a class, may increase the risk of bleeding and hypotension.

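### Eligibility does not bar patients already on IV or SQ prostacyclin, although study drug is expected to stop when such therapy is added and starting it for worsening PAH is a primary event; one exclusion line would close the gap

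*Protocol*

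**What the plan says.** Background therapy at entry is governed by few rules. Inclusion 11 reads: "Subjects receiving additional FDA approved PAH therapies must be stable on their current dose for at least 30 days prior to the Baseline Visit", with an allowance for anticoagulant and diuretic changes. Inclusion 12 requires 90 uninterrupted days of inhaled treprostinil, the last 30 at a stable dose. Of the 15 exclusions in Protocol 5.3, the only one aimed at a prostanoid is exclusion 2: "Has previous experience with beraprost or BPS-314" and its formulations. Protocol 6.7.1 refers back to 5.2 and 5.3, repeats the beraprost bar and states that nothing further is restricted. SAP 3.1 likewise permits other approved PAH therapies at a stable dose, without limiting route.

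Protocol 2.1 gives parenteral prostacyclin two roles after randomization. It is a primary event: "Initiation of a parenteral (infusion or sub-cutaneous) prostacyclin, directly related to worsening PAH". It also marks the expected end of study drug, since subjects stay on it "unless/until IV or SQ prostanoid therapy is added" or they receive a lung transplant.

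**The concern.** Read literally, the criteria admit a patient on a stable IV or SQ infusion who has also completed 90 days of inhaled treprostinil. Three things then fit badly.

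- **Safety.** The first study tablet, on Baseline Day 2, would add a third prostanoid to a systemic infusion. Section 4.1.1 is cautious even about two: "As this study is novel in the use of combined prostanoid therapy". The modelling in 1.3 used BPS-314d data with "predicted PK data for combination administration with inhaled treprostinil" and no third agent. Section 7.12.8 warns: "Prostacyclins, as a class, may increase the risk of bleeding and hypotension".
- **Hypothesis.** Section 1.4 describes "creating an effect that more closely approximates parenteral therapy than using either therapy alone". That aim does not apply to someone already receiving parenteral therapy.
- **Endpoint.** Such a patient cannot newly start a therapy already being taken, so one of the five primary components is in practice closed to them.

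**Working it through.** **1. Is there a rule elsewhere that closes the gap?**

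| Place | What it does | Bars IV/SQ prostacyclin at entry? |
|---|---|---|
| Protocol 5.2, inclusion 11 | Requires a 30-day stable dose of additional approved PAH therapy | No |
| Protocol 5.3, exclusion 2 | Bars prior beraprost products | No |
| Protocol 5.3, exclusion 5 | Bars active hemorrhage or raised hemorrhage risk from a pre-existing condition | No, it concerns conditions |
| Protocol 5.3, exclusion 14 | Illness or laboratory values, at the investigator's judgment | No, not therapy |
| Protocol 6.6 | Stable conventional therapy; examples are oral vasodilator, digoxin, oxygen | No, examples only |
| Protocol 6.7.1 | Adds nothing beyond 5.2 and 5.3 | No |
| SAP 6.7.2 | Background categories: ERA, PDE-5 inhibitor, inhaled treprostinil, riociguat | No, table categories |

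Exclusion 13 makes a useful comparison. Atrial septostomy is part of a primary component, and a previous septostomy is excluded. Parenteral prostacyclin has no matching entry rule.

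**2. The plan's own sample size.** Inputs from Protocol 10.2 and SAP 4.1: one-year event rates 45% and 25%, 1:1 allocation, accrual 1.5 years, total 2.5 years, 240 subjects, 113 events.

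- Hazards: −ln(0.55) = 0.598 and −ln(0.75) = 0.288; HR = 0.481; |ln HR| = 0.7315.
- Events for 90% power at two-sided 0.01: 4 × (2.576 + 1.282)² / 0.7315² = 111.2, so 112 (stated 113).
- Power with 113 events: Φ(0.7315 × √113/2 − z) = Φ(3.888 − z). With z = 2.576 this is 90.5%. With z = 1.960 it is 97.3% (stated 90% and 97%).
- Probability of an event by 2.5 years: 1 − (e^(−λ) − e^(−2.5λ))/(1.5λ) = 0.637 (placebo) and 0.391 (active). With 120 per arm and no dropout, 120 × (0.637 + 0.391) = 123.3 events; 113 are reached at 2.29 years.

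The plan's figures reproduce, and the added exclusion changes none of these inputs.

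**3. Illustration only.** The documents give neither the share of such patients nor the parenteral component's share of events, so every share and multiplier below is assumed. A fraction s of subjects has its event hazard multiplied by m. In the columns headed no benefit, affected subjects in both arms have the placebo hazard times m. The power is then Φ(3.888 × (1 − e) − 1.960), where e is their share of the 113 events. With full benefit, the HR is unchanged and power stays at 97.3%.

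| s | m | e, no benefit | Power at 0.05, no benefit | Shift in date of 113 events, no benefit | Same, full benefit |
|---|---|---|---|---|---|
| 2% | 0.8 | 2.2% | 96.7% | −1 day | +2 days |
| 5% | 0.7 | 5.0% | 95.9% | 0 days | +9 days |
| 10% | 0.6 | 9.0% | 94.3% | +9 days | +26 days |
| 10% | 1.4 | 14.4% | about 91% | about −38 days | about −18 days |

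The last row is included because 1.3 places parenteral therapy later in the disease, so a higher hazard is as plausible as a lower one. The fewest events expected by 2.5 years is 119.6 (s = 10%, m = 0.6, full benefit), still above 113.

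**The case against.** The strongest reply is that the gap is largely theoretical. Section 1.3 says parenteral prostacyclins are usually held back until later disease. Entry requires 90 days of inhaled treprostinil and an unsatisfactory response to it. Protocol 10.2 describes the control as inhaled treprostinil alone. The examples in 6.6 and the categories in SAP 6.7.2 contain no parenteral agent. This stands as evidence that such patients are rare and were not foreseen. It does not make the criteria exclude them, because none of these places is an eligibility rule.

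Second, the continuation wording in 2.1 describes escalation after randomization. It states an expectation, not a contraindication to the combination. That is correct. The point rests on a mismatch between 2.1 and the entry criteria, not on a prohibition.

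Third, if the motive is safety, an exclusion limited to IV and SQ routes is partial, because inclusion 11 would equally admit an additional oral or inhaled prostanoid. That is also correct. The narrower line is chosen because IV and SQ prostacyclin are the ones the protocol itself ties to the end of study drug and to a primary event.

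Fourth, safeguards exist: unblinded DSMB review, limited early recruitment at prostanoid-experienced sites, a one-tablet start, 2–3 hours of observation, and exclusion 5. They lower the risk, but none is directed at a triple combination.

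A reader might infer that the primary comparison is biased or the trial underpowered. The documents do not support that. Allocation is random within strata, so such patients fall in both arms by chance. Death, PAH hospitalization and walk-based worsening still capture their decline, and the log-rank test stays valid. Nor do the documents show that any such patient was enrolled.

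**Conclusion.** The gap holds on the text: Protocol 5.2, 5.3 and 6.7.1 allow randomization of a patient already on stable IV or SQ prostacyclin. Closing it serves patient safety and population fit. No effect on the primary test, the 113 events or the stated power is shown, and the power and timing shifts above are illustrations on unsourced inputs.

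This is a cheap, optional improvement, held with medium confidence. Two limits apply. The text of SAP 6.11 (Blinded Data Review) and the Israel amendment cited in SAP 1 were not available for this check, so either may already deal with it. The protocol expected the last visit in Q2 2016 and the SAP is dated 13 September 2018, so recruitment may be over.

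**What to change.** While recruitment is open, add one exclusion to Protocol 5.3: *Is receiving, or within 30 days before the Baseline Visit has received, an IV or SQ prostacyclin (transient use of 7 days or less for non-PAH illness, completed before Baseline, is allowed).* The 30-day look-back follows the stability period in inclusion 11, and the transient-use allowance follows the endpoint definition in 2.1. Inclusion 11, section 6.7.1, the primary analysis, the 113 events and the 240 subjects need no change.

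The cost is one line in the next amendment and a few patients on parenteral prostacyclin who can no longer be recruited.

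If enrolment is complete, check the prior-medication data at the blinded review. If such subjects are found, state in the planned SAP addendum that they leave the risk set for the parenteral-prostacyclin component analysis in SAP 6.12.7, which is exploratory. They remain in the primary analysis.
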